9 SAFETY ANALYSIS

All Safety analyses will be conducted using the Safety population.

9.1 Adverse events

Adverse events are defined in protocol Appendix 8.2.

A treatment-emergent AE (TEAE) is defined as any event not present prior to the first administration of the study drug, or any event already present that worsens in either severity or frequency following exposure to the study drug.

An AE that occurs prior to the first administration of the study drug will be considered a non-treatment emergent AE.

TEAEs will be classified and summarized as follow:

- TEAEs in pitavastatin period: TEAEs with a start date/time between first dose of pitavastatin on Day 1 and before first dose of ceftobiprole on Day 4.
- TEAEs in ceftobiprole period: TEAEs with a start date/time between first dose of ceftobiprole on Day 4 and before first dose of pitavastatin on Day 6.
- TEAEs in ceftobiprole + pitavastatin period: TEAEs with at start date/time on or after first dose of pitavastatin on Day 6.
- Overall: all TEAEs starting on or after first dose of pitavastatin on Day 1.

An overview summary of number and percentage of subjects will be provided for any TEAE, study-drug-related TEAEs, serious TEAEs, study drug-related serious TEAEs, TEAEs leading to treatment discontinuation, study drug-related TEAEs leading to treatment discontinuation, TEAEs leading to treatment interruption, study drug-related TEAEs leading to treatment interruption, TEAEs leading to death, study drug-related TEAEs leading to death. In summary tables, relationship and action taken with study drug refer to ceftobiprole or pitavastatin.

All TEAEs, non-TEAEs, serious AEs (SAEs), and AEs leading to death will be presented in separate listings.

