-1	-25.5				X		X
	-23.5				X		
	-21.5				X		
	-19.5				X		
	-17.5				X		
	-9.5				X		
1	Predose Pitavastatin		X		X		X
	0	Day 1 Pitavastatin Dosing					
	0.25		X				
	0.5		X				
	0.75		X				
	1		X				
	1.5		X				
	2		X				X
	2.5		X				
	3		X				
	4		X				
	6		X				
	8		X				
	10		X				
	12		X				
2	24		X				X
	36		X				
3	48		X				X
4	Predose Ceftobiprole			X			X
	70.5	Start Day 4 First Ceftobiprole Infusion					
	72.5	End Day 4 First Ceftobiprole Infusion		X (Immediately After Stopping Day 4 First Ceftobiprole Infusion)		X (Prior to Stopping Day 4 First Ceftobiprole Infusion)	X (Prior to Stopping Day 4 First Ceftobiprole Infusion)
	78.5	Start Day 4 Second Ceftobiprole Infusion					

Day	Time Point With Day 1 Pitavastatin Dosing as Baseline (hours)	Dose	PK of Pitavastatin and Metabolite	Ceftobiprole PK	CP-I Bood Sampling	12-Lead ECG	Vital Signs
	80.5	End Day 4 Second Ceftobiprole Infusion					
	86.5	Start Day 4 Third Ceftobiprole Infusion					
	88.5	End Day 4 Third Ceftobiprole Infusion					
5	Predose Ceftobiprole			X	X (Prior to Starting Day 5 First Ceftobiprole Infusion)		X (Prior to Starting Day 5 First Ceftobiprole Infusion)
	94.5	Start Day 5 First Ceftobiprole Infusion					
	95.5			X			
	96.5	End Day 5 First Ceftobiprole Infusion		X (Immediately After Stopping Day 5 First Ceftobiprole Infusion)	X		
	98.5			X	X		
	100.5			X	X		
	Predose Ceftobiprole			X (Prior to Starting Day 5 Second Ceftobiprole Infusion)	X (Prior to Starting Day 5 Second Ceftobiprole Infusion)		
	102.5	Start Day 5 Second Ceftobiprole Infusion					
	104.5	End Day 5 Second Ceftobiprole Infusion					
	Predose Ceftobiprole				X (Prior to Starting Day 5 Third Ceftobiprole Infusion)		
	110.5	Start Day 5 Third Ceftobiprole Infusion					

Day	Time Point With Day 1 Pitavastatin Dosing as Baseline (hours)	Dose	PK of Pitavastatin and Metabolite	Ceftobiprole PK	CP-I Blood Sampling	12-Lead ECG	Vital Signs
	112.5	End Day 5 Third Ceftobiprole Infusion					
6	Predose Ceftobiprole			X (Prior to Starting Day 6 First Ceftobiprole Infusion)			X (Prior to Starting Day 6 First Ceftobiprole Infusion)
	118.5	Start Day 6 First Ceftobiprole Infusion					
	119.5			X			
	Predose Pitavastatin		X		X (Prior to Day 6 Pitavastatin Dosing)		
	120	Day 6 Pitavastatin Dosing					
	120.25		X				
	120.5	End Day 6 First Ceftobiprole Infusion	X	X (Immediately After Stopping Day 6 First Ceftobiprole Infusion)		X (Prior to Stopping Day 6 First Ceftobiprole Infusion)	X (Prior to Stopping Day 6 First Ceftobiprole Infusion)

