4 GENERAL STATISTICAL CONSIDERATIONS

Summary outputs will be presented overall, except adverse events that will be summarized by period (see Section 9.1 for details) and overall. No formal hypothesis testing will be performed. Continuous data, unless otherwise specified, will be described using descriptive statistics (n, mean, standard deviation [SD], median, minimum, and maximum). Categorical data will be described using the subject count and percentage in each category. Non-zero percentages will be rounded to one decimal place, except 100%, which will be displayed without any decimal places. For the summary statistics of all numerical variables unless otherwise specified, minimum and maximum will be displayed to the same level of precision as reported, up to a maximum of three decimal places. Mean and median will be displayed to one level of precision greater than the data collected, up to a maximum of three decimal places. Standard deviation will be displayed to two levels of precision greater than the data collected, up to a maximum of three decimal places.

When count data are presented, the percentage will be suppressed when the count is zero, to draw attention to the non-zero counts. A row denoted 'Missing' will be included in count tabulations where specified in the table shells, to account for dropouts and missing values. The denominator for all percentages will be the number of subjects in the population of interest, unless otherwise specified.

All data will be displayed in listings sorted by subject ID and treatment periods, when applicable.

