12 APPENDICES

Appendix 1 Adverse event and prior/concomitant medication date imputations

Imputation rules for partial dates

Adverse event start date imputation

Parameter	Missing	Additional conditions	Imputation
Start date for AEs	D	M and Y same as M and Y of first dose of study drug	Date of first dose of study drug
		M and/or Y not same as date of first dose of study drug	First day of month
	D and M	Y same as Y of first dose of study drug	Date of first dose of study drug
		Y is after Y of first dose	1 January
	D, M, Y	None – date completely missing	Date of first dose of study drug

D = day; M = month; Y = year; AE = adverse event.

Note: In all cases, if an estimated start date is after a complete stop date, use the first day of the stop date month.

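### The adverse-event tables set a 49.5-hour ceftobiprole period beside a combination period with no stated end, and a pre-Day 1 event that worsens on study can fall into no column

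*SAP*

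**What the plan says.** SAP section 9.1 sorts treatment-emergent events into three consecutive periods by start date and time:

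- pitavastatin: "TEAEs with a start date/time between first dose of pitavastatin on Day 1 and before first dose of ceftobiprole on Day 4";
- ceftobiprole: "TEAEs with a start date/time between first dose of ceftobiprole on Day 4 and before first dose of pitavastatin on Day 6";
- combination: "TEAEs in ceftobiprole + pitavastatin period: TEAEs with at start date/time on or after first dose of pitavastatin on Day 6".

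A fourth category is "Overall: all TEAEs starting on or after first dose of pitavastatin on Day 1". The output is counts and percentages of subjects; no measure per unit of time at risk is planned. SAP section 4 adds: "The denominator for all percentages will be the number of subjects in the population of interest, unless otherwise specified". Section 9 uses the Safety population, which section 4.2.1 defines by receipt of at least one dose of study drug.

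The SAP gives the combination period no end. Protocol section 3.5.1.3.1 stops active event collection at Follow-up, and section 3.1.4 puts that visit at Day 15 ± 2, that is, 5 to 9 days after the Day 8 discharge.

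The definition of a treatment-emergent event in SAP section 9.1 includes an existing event that gets worse after exposure. The sentence after it classes any event occurring before the first dose as not treatment-emergent and makes no exception for worsening.

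**The concern.** One secondary objective is the safety of ceftobiprole without and with a single dose of pitavastatin. With no hypothesis test planned, the ceftobiprole and combination columns side by side are the main summary for that objective. A crude percentage of subjects with an event grows with the time over which events are counted. If one column counts for about two days and its neighbour for seven to eleven, a difference between them may reflect only time.

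The second issue is completeness. A definition that admits worsening, combined with columns that admit only events starting on or after Day 1 dosing, can leave a treatment-emergent event in no summary column.

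A third, smaller issue is the denominator: a subject who stops before a period begins is still counted in that period's percentages.

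**Working it through.** **Inputs.** From Protocol Table 2, in hours after the Day 1 pitavastatin dose:

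- "Start Day 4 First Ceftobiprole Infusion": 70.5 h
- "Day 6 Pitavastatin Dosing": 120 h
- end of the last infusion on Day 7: 160.5 h
- last Day 8 assessment: 168 h

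Follow-up is on Day 13 to Day 17, nominally Day 15.

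**Reproducing the plan's own figures.** Day 4 infusion start: 3 × 24 − 1.5 = 70.5 h. Day 6 dose: 5 × 24 = 120 h. Follow-up after discharge: 13 − 8 = 5 and 17 − 8 = 9 days. Longest participation, with no Day 0: 21 + 17 = 38 days. All agree with the protocol.

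**Window lengths**, with Follow-up taken at the clock time of dosing:

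- Pitavastatin: 70.5 − 0 = 70.5 h.
- Ceftobiprole: 120 − 70.5 = 49.5 h (2.06 days).
- Combination: (13 − 6) × 24 = 168 h to (17 − 6) × 24 = 264 h; nominally (15 − 6) × 24 = 216 h.
- Combination over ceftobiprole: 168/49.5 = 3.4; 216/49.5 = 4.4; 264/49.5 = 5.3.

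**Share of the combination window after the last infusion.** Infusions continue until 160.5 − 120 = 40.5 h into it. The remainder is 1 − 40.5/168 = 76% to 1 − 40.5/264 = 85%. The protocol gives half-lives of 3 to 4 h for ceftobiprole and about 12 h for pitavastatin. Five half-lives end by 160.5 + 5 × 4 = 180.5 h and 120 + 5 × 12 = 180 h, whereas Follow-up falls at 288 to 384 h.

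**Effect on a crude percentage.** The documents give no event rate, so a constant rate r per subject-day, the same in every period, is assumed for illustration. The expected share of subjects with at least one event over d days is 1 − exp(−r × d).

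| Assumed r | Ceftobiprole (49.5 h) | Combination, current rule (168–264 h) | Combination closed at 168 h (48 h) |
|---|---|---|---|
| 1% | 2.0% | 6.8–10.4% | 2.0% |
| 2% | 4.0% | 13.1–19.7% | 3.9% |
| 5% | 9.8% | 29.5–42.3% | 9.5% |
| 10% | 18.6% | 50.3–66.7% | 18.1% |

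With no true difference, the combination percentage is 2.7 to 5.1 times the ceftobiprole percentage. At 5% that is about 1.2 against 3.5 to 5.1 of 12 subjects. Closing the column at 168 h gives 168 − 120 = 48 h, and 48/49.5 = 0.97.

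**Worsening.** Two cases follow from the text of section 9.1, if a worsened event keeps its original start date:

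- Began before Day 1, worsens after dosing: treatment-emergent by the definition, not treatment-emergent by the next sentence, and outside all three periods and Overall.
- Began on study, worsens in a later period: counted in the period where it started and in Overall, but not in the later period.

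**Denominator.** If one of 12 subjects leaves before Day 4 and is not replaced, 11 are at risk but percentages are taken over 12, a relative dilution of 1/12 = 8%. With a replacement it is 12 over 13, or 1/13 = 8%. The factor is the same in the ceftobiprole and combination columns.

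**The case against.** The strongest reply is that this is a matter of display. The SAP is to be read with the protocol, which ends active collection at Follow-up, so the last window is finite. The safety analysis is descriptive, in 12 subjects of an exploratory study. Drug-related events are tabulated separately, and full listings would let anyone regroup events by start time. In a fixed-sequence design the columns are confounded with calendar time and cumulative ceftobiprole dosing whatever their length. The inflation figures also assume one constant rate, although observation falls from daily inpatient monitoring to a single visit after discharge. All of this is fair and limits the harm. It does not make the two percentages comparable, and section 9.1 carries no caution about window length. Nor is ascertainment clearly lower overall in the longer window: it has two scheduled laboratory tests (Day 7 and Follow-up) and two ECGs (Day 6 and Follow-up), against one of each for ceftobiprole alone (Days 5 and 4).

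Three stronger readings are tempting but not supported:

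- A reader might infer that every worsening event is lost. An on-study event stays in its starting period and in Overall, and the severity table in section 9.1.3 takes the most severe occurrence. Only pre-Day 1 events can vanish, and only if worsening is not recorded with a new start date, which the documents do not settle.
- A reader might infer that the denominator rule removes events or biases the comparison of ceftobiprole without and with pitavastatin. It removes none, and a drop-out before Day 4 dilutes both columns equally.
- A reader might infer from SAP Appendix 1 that any start date missing its day goes to pitavastatin alone. That imputation to the first-dose date applies when "M and Y same as M and Y of first dose of study drug"; otherwise the first of the month is used. Subjects are confined and monitored daily from Day −2 to Day 8, so missing days should be few. This is not part of the point.

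**Conclusion.** The point holds on two counts. First, the SAP sets crude percentages from a 49.5 h period beside those from a period of 168 to 264 h, most of it after the last infusion. The window lengths are exact; the size of the distortion rests on an assumed constant and equal event rate. Second, the two sentences on treatment emergence conflict, and a pre-Day 1 event that worsens and keeps its start date is counted in no column. The denominator rule is a minor addition.

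A reader might infer that all these rules push the safety comparison one way. They do not. The long window raises the combination percentage, while leaving a worsened event in its earlier period lowers it, so no net direction can be stated for all of them together. What can be said is that window length alone favours ceftobiprole without pitavastatin. The consequence is confined to descriptive safety tables; the primary pharmacokinetic analysis and the CP-I analysis are untouched.

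**What to change.** In SAP section 9.1:

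- Split the last period into an on-treatment combination column, from the Day 6 pitavastatin dose to the Day 8 assessments (168 h), and a follow-up column. Keep every event, including abnormalities first found at Follow-up, in Overall and in the listings.
- Reconcile the definition of a treatment-emergent event with the sentence on pre-dose events. Assign events to periods, and to Overall, by date and time of onset or worsening, and state how a worsening is recorded.
- Use the number of subjects dosed in each period as that period's denominator.

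The cost is SAP wording and one table column; study conduct and the assessment schedule do not change, provided the case report form records when an event worsened. The downside is small: events first seen after Day 8 appear under follow-up and not under the combination. Some drug may still be present at the cut, which falls 168 − 160.5 = 7.5 h after the last infusion and 48/12 = 4 pitavastatin half-lives after the dose. A table footnote should say so.

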	120.75		X				
	121		X				
	121.5		X				
	122		X				
	122.5		X	X			
	123		X				
	124		X				
	124.5			X			
	126		X				
	Predose Ceftobiprole			X (Prior to Starting Day 6 Second Ceftobiprole Infusion)			
	126.5	Start Day 6 Second Ceftobiprole Infusion					
	128		X				
	128.5	End Day 6 Second Ceftobiprole Infusion					
	130		X				

Day	Time Point With Day 1 Pitavastatin Dosing as Baseline (hours)	Dose	PK of Pitavastatin and Metabolite	Ceftobiprole PK	CP-I Bood Sampling	12-Lead ECG	Vital Signs
	132		X				
	134.5	Start Day 6 Third Ceftobiprole Infusion					
	136.5	End Day 6 Third Ceftobiprole Infusion					
7	Predose Ceftobiprole			X (Prior to Starting Day 7 First Ceftobiprole Infusion)			X (Prior to Starting Day 7 First Ceftobiprole Infusion)
	142.5	Start Day 7 First Ceftobiprole Infusion					
	144		X				
	144.5	End Day 7 First Ceftobiprole Infusion					
	156		X				
	150.5	Start Day 7 Second Ceftobiprole Infusion					
	152.5	End Day 7 Second Ceftobiprole Infusion					
	158.5	Start Day 7 Third Ceftobiprole Infusion					
	160.5	End Day 7 Third Ceftobiprole Infusion					
8	168		X				X
Follow-up/Early Termination						X	X

CP-I=coproporphyrin I; ECG=electrocardiogram; PK=pharmacokinetic(s)

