### 3.1.4 Follow-up / Early Termination

The follow-up assessments will be performed 5 to 9 days after discharge on Day 8 (Day 15 ± 2 days) or 5 to 9 days after the time of Early Termination.

Assessments during Follow-up/Early Termination will be performed as presented in the schedule of assessments (Table 1).

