#### **3.5.1.3.1 Adverse Events**

The time period for actively eliciting and collecting AEs and SAEs ('active collection period') for each subject begins from the time the subject provides informed consent, which is obtained before undergoing any study-related procedure and/or receiving study intervention), up to and including Follow-up.

Any clinically significant observations, as determined by the Investigator, in the results of clinical laboratory tests, 12-lead ECGs, vital signs measurements, or physical examinations will be recorded as AEs.

A treatment-emergent adverse event (TEAE) is defined as any event not present prior to the first administration of the study drug, or any event already present that worsens in either severity or frequency following exposure to the study drug.

An AE that occurs prior to the first administration of the study drug will be considered a pre-treatment AE.

At several time points before and after drug administration, subjects will be asked non-leading questions to determine the occurrence of AEs. Subjects will be asked in general terms about any AEs at regular intervals during the study. In addition, all AEs reported spontaneously during the course of the study will be recorded. All AEs will be recorded in the eCRF as reported terms.

The severity of the AEs will be graded in accordance with the Common Terminology Criteria for Adverse Events (CTCAE v5.0); the relationship between the AEs and the study drug will be indicated as related or not related. Details on grading the severity of AEs and assessing the relationship to study treatment are given in Appendix [8.2](#).

For subjects who are screening failures, the active collection period ends when screening failure status is determined.

If a subject withdraws from the study and also withdraws consent for the collection of future information, the active collection period ends when consent is withdrawn.

If a subject either permanently or temporarily discontinues participation in the study because of an AE or SAE, the event must be recorded in the eCRF, and if an SAE, reported using the SAE Report Form.

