2.2 Secondary objectives

The secondary objectives are:

- To assess the pharmacodynamic (PD) effect of iv ceftobiprole on the diurnal plasma level profile of coproporphyrin I (CP-I) in healthy subjects
- To describe the systemic exposure of iv ceftobiprole without and with oral administration of pitavastatin in healthy subjects
- To assess the single-dose plasma PK of the pitavastatin metabolite, pitavastatin lactone, after a single oral dose of pitavastatin, administered without and with iv ceftobiprole in healthy subjects
- To assess the safety and tolerability of ceftobiprole without and with administration of a single oral dose of pitavastatin in healthy subjects.

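### SAP 9.1 leaves the 'ceftobiprole + pitavastatin' adverse-event period open to Follow-up, 3.4 to 5.3 times as long as the ceftobiprole-alone period, which tilts unadjusted percentages towards the combination if background events are steady

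*SAP*

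**What the plan says.** SAP 2.2 lists this secondary objective: "To assess the safety and tolerability of ceftobiprole without and with administration of a single oral dose of pitavastatin in healthy subjects". SAP 4 says that adverse events are summarized by period and overall, and refers to SAP 9.1 for the periods.

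SAP 9.1 assigns each event to a period by its onset. The pitavastatin period closes at the first ceftobiprole dose. The ceftobiprole period is closed at both ends: "TEAEs with a start date/time between first dose of ceftobiprole on Day 4 and before first dose of pitavastatin on Day 6". The combination period has a start only: "TEAEs in ceftobiprole + pitavastatin period: TEAEs with at start date/time on or after first dose of pitavastatin on Day 6".

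Protocol 3.5.1.3.1 collects adverse events "up to and including Follow-up". Protocol 3.1.4 places that visit "5 to 9 days after discharge on Day 8 (Day 15 ± 2 days".

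The overview summary in SAP 9.1 and the incidence tables in SAP 9.1.1 give the number and percentage of subjects. Neither document gives an on-treatment cut-off, a separate follow-up column or a rate per unit of time. SAP 3.1.3 ends Period 2 on Day 8.

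**The concern.** The ceftobiprole column and the combination column are the two that bear on the without/with objective. A subject's chance of at least one event grows with the time observed, and the two columns cover very different lengths of time. The longer one includes the days after discharge, when no study drug is given and subjects are no longer confined, and it runs 5 to 9 days past the SAP's own end of Period 2. It also takes in the Follow-up laboratory tests and ECG. Under Protocol 3.5.1.3.1, clinically significant findings at those checks are recorded as adverse events.

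Background events could therefore be tabulated as events on the combination. At stake is how the summary tables for a secondary safety objective are read. No test or error rate is involved, because SAP 4 plans no formal hypothesis testing.

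**Working it through.** **Inputs**

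- Start of the ceftobiprole period, in hours after the Day 1 tablet: "70.5 Start Day 4 First Ceftobiprole Infusion" (Protocol Table 2).
- Its end, which is the start of the combination period: "120 Day 6 Pitavastatin Dosing" (Protocol Table 2).
- Last exposure: "End Day 7 Third Ceftobiprole Infusion", at 160.5 h (Protocol Table 2).
- Discharge on Day 8; the last scheduled sample is at clock time 168 h (Protocol Table 2).
- Half-lives: ceftobiprole 3 to 4 h (Protocol 1.1.1.1); pitavastatin about 12 h (Protocol 3.2).
- Subjects: 12 (SAP 3.1.2).
- Background event rate: not in the documents. Assumed range 0.01 to 0.1 per subject-day.

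**The plan's own figure.** Day 15 ± 2 measured from Day 8 gives 15 − 2 − 8 = 5 and 15 + 2 − 8 = 9 days. This agrees with Protocol 3.1.4.

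**Period lengths**

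- Ceftobiprole alone: 120 − 70.5 = 49.5 h.
- Combination: (Follow-up day − 6) × 24 h.
- Five half-lives after last exposure: ceftobiprole 160.5 + 5 × 4 = 180.5 h; pitavastatin 120 + 5 × 12 = 180 h. Both have passed by 180.5 h, which is 60.5 h after the Day 6 tablet.

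| Follow-up | Combination length | Ratio to 49.5 h | Share after last infusion, (length − 40.5)/length | Share after five half-lives, (length − 60.5)/length |
|---|---|---|---|---|
| Day 13 | 168 h | 3.4 | 76% | 64% |
| Day 15 | 216 h | 4.4 | 81% | 72% |
| Day 17 | 264 h | 5.3 | 85% | 77% |

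**Effect of length alone.** Assume a constant rate r per subject-day and no pitavastatin effect. The expected share of subjects with an event is 1 − exp(−r × days), with 49.5/24 = 2.0625 days against 9 days (Follow-up on Day 15). The last column is the chance that the combination shows more events among 12 subjects, using Poisson counts, for Follow-up on Day 13 to Day 17.

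| Assumed r | Ceftobiprole alone | Combination | Chance of more events on combination |
|---|---|---|---|
| 0.01 | 2.0% | 8.6% | 0.48 to 0.65 |
| 0.02 | 4.0% | 16.5% | 0.67 to 0.83 |
| 0.05 | 9.8% | 36.2% | 0.86 to 0.97 |
| 0.1 | 18.6% | 59.3% | 0.96 to more than 0.99 |

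At r = 0.05 this is 12 × 0.098 = 1.2 subjects against 12 × 0.362 = 4.3.

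**If events arise only while drug is present.** The effective combination window is then 40.5 h (to the end of the last infusion) to 60.5 h (adding five half-lives). The ratio to 49.5 h is 0.82 to 1.22. For assumed rates of 0.05 to 0.2 per subject-day, the chance of more events on the combination falls to about 0.30 to 0.57.

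**With a cut at Day 8 discharge.** 168 − 120 = 48 h, and 48/49.5 = 0.97. At r = 0.05 the expected share is 1 − exp(−0.05 × 2) = 9.5%, against 9.8%. The part after discharge lasts 120, 168 or 216 h for Follow-up on Day 13, 15 or 17.

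**The case against.** Several points against the concern have force.

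- *The display is descriptive.* The SAP specifies no difference, ratio or test between periods. This stands, and it limits the consequence to how the tables read.
- *The direction is not guaranteed.* The documents give no event rate. First ceftobiprole exposure falls in the ceftobiprole-alone period, so common reactions named in Protocol 1.2, such as nausea, phlebitis or dysgeusia, could cluster there. This stands.
- *Other outputs soften the bias.* All events are listed, and with 12 subjects each late onset can be looked at individually. Drug-related events are tabulated separately, and Protocol 8.2.1 asks the investigator to weigh timing relative to dosing. Late events are less likely to be judged related, so those tables should be less distorted. This stands.
- *Attribution to the last treatment given is a recognised and cautious convention.* It keeps delayed reactions with the treatment, and Protocol 1.2 names hepatic enzyme increases and *C. difficile* colitis among the risks. This is a good reason to retain the sponsor's column as a total. It does not justify reading that column against one of 49.5 h without stating the lengths.
- *A Day 8 cut is not a clean drug-free boundary.* About 180.5 − 168 = 12.5 h of residual exposure falls after it. The only scheduled laboratory draw between the Day 6 tablet and discharge is on the morning of Day 7, and no ECG is scheduled between Day 6 and Follow-up. Later findings would first appear after the cut. This stands and shapes the fix.

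A reader might infer that the table will show more events on the combination even if pitavastatin adds nothing, or that a true signal could not be told from longer observation. The documents support neither. The first needs a steady and not very low background rate. The second overlooks the listings and the drug-related tables.

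**Conclusion.** The point holds as a length bias in a descriptive display. The combination period is 3.4 to 5.3 times as long as the ceftobiprole-alone period, and about 64% to 77% of it falls after five half-lives of both drugs. These figures rest only on the schedule and the half-lives stated in the protocol.

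The size of the effect on the percentages depends on an assumed constant background rate. With 12 subjects an excess on the combination is likely at 0.05 events per subject-day, roughly even odds to two in three at 0.01, and absent or reversed if events occur only on drug or cluster at the first ceftobiprole infusions. No other section of either document corrects the imbalance. The change is worth making because it is cheap. It does not affect the primary pharmacokinetic analysis.

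**What to change.** In SAP 9.1, keep the sponsor's combination column as a total and split it by onset:

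- (a) Day 6 pitavastatin dose to Day 8 discharge, the end of Period 2 (about 48 h), to be read against the 49.5 h ceftobiprole column;
- (b) after discharge to Follow-up.

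State the length of every period in the table header. Footnote that (b) includes about 12.5 h of residual drug exposure and any laboratory or ECG finding first detected at Follow-up, and do not label it drug-free. Leave the Overall column and the listings unchanged.

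Cost: SAP wording and one or two extra table columns. Data collection and study conduct do not change. The downside is that some late or late-detected drug effects will appear in (b) rather than (a). They remain in the combination total, in Overall and in the listings.
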